4. SELECTION AND WITHDRAWAL OF PATIENTS

Prospective waivers (exceptions) from study inclusion and exclusion criteria to allow patients to be enrolled are not granted by Teva ([Appendix C](#)).

Changes to inclusion or exclusion criteria are detailed in Section [16](#).

4.1. Patient Inclusion Criteria

Patients may be randomized/enrolled in this study only if they meet all of the following criteria:

- a. The patient is 13 years or older at the time of screening.
- b. The patient has a documented diagnosis of asthma established at the investigational center at the time of informed consent or the investigator confirms a diagnosis of asthma.
- c. The patient is currently on treatment with an ICS with a long-acting beta₂ agonist (LABA).
- d. The patient has an ACT score of less than 19 at the screening or baseline visit.
- e. The patient is currently using inhaled albuterol sulfate as rescue medication and is willing to discontinue all other rescue medications and replace them with the study-provided Albuterol eMDPI.
- f. [Revision 1] The patient can read and communicate in English and is familiar with and is willing to use his/her own smart device that meets the minimum App requirements and download and use the App.
- g. The patient is able to provide written informed consent.
- h. The patient must be willing and able to comply with study requirements and restrictions and to remain at the investigational center for the required duration during the study period, and willing to return to the investigational center for the follow-up procedures and assessments as specified in this protocol.

4.2. Patient Exclusion Criteria

Patients will not be randomized/enrolled in this study if they meet any of the following criteria:

- a. The patient has any clinically significant uncontrolled medical condition (treated or untreated) other than asthma, which in the view of the investigator would preclude participation.
- b. The patient was hospitalized for severe asthma in the last 30 days.
- c. The patient has any medical or psychiatric condition that, in the opinion of the investigator, could jeopardize or would compromise the patient's ability to participate in this study.
- d. The patient has a diagnosis of Chronic Obstructive Pulmonary Disease (COPD) or Asthma-COPD Overlap (ACO).
- e. The patient is a current smoker or has a greater than 10 pack-year history of smoking.

- f. The patient is currently being treated with systemic corticosteroids (oral, intramuscular, or intravenous) or has been treated within the last 30 days.
- g. [Revision 1] The patient has any treatment with biologics for asthma (eg, omalizumab, anti-interleukin (IL) 5, anti-IL5R, anti-IL4R), or has had such treatment within the last 90 days. (However, during the study, patients can be escalated to therapy with such agents if clinically indicated in the judgment of the investigator as part of their asthma management and remain in the study.)
- h. The patient has a known hypersensitivity to any components of the IMPs stated in this protocol.
- i. [New criterion] The patient has previously participated in a Digihaler study or is currently being treated prior to enrollment with a digital inhaler system, including the Digihaler system or an external “bolt on” digital system designed to monitor inhaler usage, such as the Propeller Health or Adherium systems.

4.3. Withdrawal Criteria and Procedures for the Patient

Each patient is free to withdraw from the study or discontinue from IMP or using the devices at any time, without prejudice to their continued care. Patient must be withdrawn from the study if any of the following events occur:

1. Patient withdraws consent or requests discontinuation from the IMP or withdrawal from the study for any reason.
2. Patient develops an illness that would interfere with his/her continued participation.
3. Patient is noncompliant with the study procedures and assessments or administration of Albuterol eMDPI, in the opinion of the investigator.
4. Patient takes prohibited concomitant medications as defined in this protocol (ie, other SABA products).
5. The sponsor requests withdrawal of the patient.
6. Patient experiences an adverse event or other medical condition which indicates to the investigator that continued participation is not in the best interest of the patient.

Patients should be treated with standard of care after withdrawal from or termination of the study as appropriate.

Investigators should attempt to obtain information on patients in the case of withdrawal from the study or discontinuation from IMP. Results of any evaluations and observations, together with a narrative describing the reason(s) for withdrawal from the study or discontinuation from IMP, must be recorded in the source documents. The case report form (CRF) must document the primary reason for withdrawal from the study or discontinuation from IMP.

See [Appendix E](#) for information regarding how the study will define and address patients who are lost to follow-up to help limit the amount and impact of missing data.

If the reason for withdrawal from the study or discontinuation from IMP is an adverse event and/or adverse device effect, monitoring will be continued as applicable (eg, until the event has resolved or stabilized, until the patient is referred to the care of a healthcare professional, or until

a determination of a cause unrelated to the IMP or study procedure is made). The specific event or test result (including repeated test results, as applicable) must be recorded both on the source documentation and in the CRF; the adverse events page and/or adverse device effect page and the termination page of the CRF will be completed at that time. The investigator must inform the contract research organization (CRO) as soon as possible of each patient who is being considered for withdrawal due to adverse events. Additional reports must be provided when requested.

If a patient is withdrawn from the study or discontinues IMP for multiple reasons that include adverse events, the relevant page of the CRF should indicate that the withdrawal was related to an adverse event. An exception to this requirement will be the occurrence of an adverse event that in the opinion of the investigator is not severe enough to warrant discontinuation but that requires the use of a prohibited medication, thereby requiring discontinuation of the patient. In such a case, the reason for discontinuation would be “need to take a prohibited medication,” not the adverse event.

In the case of patients lost to follow-up, attempts to contact the patient must be made and documented in the patient’s medical records and transcribed to the CRF.

All assessments should be performed according to the protocol for the end of treatment visit or upon early termination if possible. Patients are required to return the Albuterol eMDPI (used and unused) upon withdrawal from the study.

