5.6. Prior and Concomitant Medication or Therapy

Any concomitant medication a patient is taking at screening and up to the final visit will be recorded on the CRF. Trade name and international nonproprietary name (if available), indication, dose, and start and end dates of the administered medication will be recorded. The sponsor will encode all medication according to the World Health Organization (WHO) drug dictionary (WHO Drug).

The use of other SABA products, by the DS group, is prohibited during this study except for the use of nebulized albuterol, as needed, in the ED for an acute exacerbation of asthma.

At the end of treatment visit (Visit 2), patients will be asked whether they have taken any medications (other than IMP), including over-the-counter medications, vitamins, or herbal or nutritional supplements, since the previous visit.

Concomitant medication and treatment will be recorded through the final visit.

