9.1. Sample Size and Power Considerations

[figure not shown]
Sample size estimates are based upon the assumption that the absolute differences between the DS and CC groups and the associated operational characteristics will be similar to the absolute differences and operational characteristics of the DS and CC groups noted in the sample size rationale for the study design.

The recommended sample size for the study is 150 evaluable patients per group (30 investigational centers with each investigational center enrolling at least 10 patients), 300 patients in total. Accounting for a dropout rate of 10%, this leads to a recommended total number of 330 enrolled patients.

With this sample size and assuming a true absolute difference in proportions (treatment effect as the estimated response rate for the CC group is 60% and for the DS group is 73%) between the groups of at least 13%, the probability that the posterior probability will be at least 95% is 0.77 (power) (analogous to 1-sided p-value < 0.05) ([Merchant et al 2016](#)). Assuming no treatment effect (difference in proportions between the groups is 0%, ie, Type 1 error) then the probability is 0.05 that posterior probability will be at least 95% is 0.05.

It should be noted that both power and Type 1 error are dependent on the absolute difference between the DS and the CC groups as illustrated in [Figure 5](#) below by the operational characteristics calculated for the study design:

Figure 5: Operational Characteristics Calculated for the Study Design

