4.3. Handling Withdrawals and Missing Data

For the primary endpoint, patients who discontinue early due to technology failure, disliking the digital platform, disease worsening, adverse experience or disliking the IMP will be counted as treatment failures. For those who discontinue early not to these reasons, the ACT value assessed at ET visit will be used. Those who discontinue early and do not have an ET visit will be counted as treatment failures.

For the SUS items 1, 3, 5, 7, and 9, if response to 1 item is missing, the missing item will be replaced by the average of the remaining 4 responses. For items 2, 4, 6, 8, and 10, if response to 1 item is missing, the missing item will be replaced by the average of the remaining 4 responses. If response to 2 or more of items 1, 3, 5, 7, and 9 are missing, or 2 or more of items 2, 4, 6, 8, and 10 are missing, the overall SUS score will be set to missing.

For the BMQ subscales, if response to 1 item within a subscale is missing, the missing response will be replaced with the average of the remaining responses within the subscale. If response to 2 or more items within a subscale are missing, the missing responses will not be replaced and the subscale score will be set to missing.

For the BIPQ cognitive subscale, if response to 1 item within the subscale is missing, the missing response will be replaced with the average of the remaining responses within the subscale. If response to 2 or more items within the subscale is missing, the missing responses will not be replaced and the subscale score will be set to missing. For the emotional subscale, if 1 of the responses is missing then the subscale will be set to missing.

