6.2.3. Sensitivity Analysis

Sensitivity analysis will be performed for the primary analysis by imputing missing ACT values using the multiple imputation (MI) method assuming missing at random (MAR). Those who discontinue early due to technology failure, disliking the digital platform, disease worsening, adverse experience or disliking the IMP will be considered having missing data. For those who discontinue early not due to these reasons, the ACT value assessed at the ET visit will be used. Those who discontinue early and do not have an ET visit will be considered having missing data.

The following steps will be performed for the analysis:

- Create complete datasets using imputation. The SAS code is as follows:

```
proc mi data = yy out = yy2 seed = 4192 n impute = 500 minimum = 5 maximum = 25;
class trt;
```

```
var trt actbase v2;  
monotone regpmm;  
run;
```

- For each dataset, the clinically important improvement in asthma control variable will be derived for each patient as defined in Section 6.2.1.
- Analyze each dataset using the model described below for the primary endpoint.

```
ods output Diffs = dif LSMeans = lsm;  
proc genmod data = indata;  
by _imputation_;  
class trt;  
model y = trt actbase / dist = binomial;  
lsmeans trt/pdiff cl diff exp;  
run;  
ods output close;
```

- The output datasets from the above analysis will contain odds ratio estimates from each of the 500 datasets. An overall estimate will be generated using PROC MIANALYZE . The SAS code is as following:

```
proc mianalyze data=zz;  
modeleffects estimate;  
stderr stderr;  
ods output paramestimates=or;  
run;
```

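### A DS-group exit recorded as need for a prohibited medication bypasses the failure rule, even when an adverse event or asthma worsening led to it

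*Protocol*

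**What the plan says.** **How the exit is recorded.** Protocol 4.3 requires the CRF to carry the primary reason for withdrawal. If there are several reasons and one is an adverse event, the exit is recorded as related to the adverse event. There is one exception: an event that the investigator considers not severe enough to justify stopping but "that requires the use of a prohibited medication, thereby requiring discontinuation of the patient". The recorded reason is then the need for the medication, not the event.

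**What is prohibited, and for whom.** Protocol 4.3 (withdrawal item 4) identifies prohibited medication as other SABA products. Protocol 5.6 limits this to one arm: "The use of other SABA products, by the DS group, is prohibited during this study", with an exemption for nebulized albuterol in the emergency department. Protocol 5.5 adds no further medication restriction.

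**How the exit is scored.** SAP 4.3 and 6.2.2 list five reasons that count as failure: technology failure, dislike of the digital platform, dislike of the IMP, disease worsening and adverse experience. For the rest, SAP 4.3 says: "For those who discontinue early not to these reasons, the ACT value assessed at ET visit will be used". SAP 4.3 also fails any early exit without an ET visit.

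**Sensitivity analysis.** SAP 6.2.3 sets exits for the five listed reasons to missing and imputes them. For the others it repeats the ET rule: "For those who discontinue early not due to these reasons, the ACT value assessed at the ET visit will be used".

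**The concern.** The failure list is there so that a patient who leaves because of an adverse event or worsening asthma is not credited with a response. The coding exception can remove that label from some of these patients. The prohibited class is asthma rescue medication, so the event behind the need will often be asthma symptoms. Protocol 7.1.1 itself treats asthma worsening that leads to discontinuation as an adverse event.

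The route exists in one arm only. A CC patient who uses a different SABA breaks no rule, stays in the study and is judged at week 12. The DS patient is withdrawn and judged on an earlier ACT, and no minimum time on treatment is set for that ACT. Which label applies depends on the investigator's opinion of severity, in an open-label trial. At stake is whether the responder status of a few DS patients follows from what happened to them or from the box ticked on the CRF.

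**Working it through.** **1. Trace one patient.** A DS patient has an adverse event judged mild enough to continue, but needs another SABA.

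| Step | Source | Result |
|---|---|---|
| Is the medication prohibited? | Protocol 5.6 | Yes in DS, no in CC |
| Recorded reason for exit | Protocol 4.3, exception | Need for a prohibited medication |
| On the failure list? | SAP 4.3, 6.2.2 | No |
| No ET visit | SAP 4.3 | Failure |
| ET visit, ACT below 20 and gain below 3 | SAP 6.2.1 | Failure |
| ET visit, ACT at least 20 or gain of at least 3 | SAP 6.2.1 | Responder |
| Handling in the sensitivity analysis | SAP 6.2.3 | Same ET ACT is used |

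Only the second-last row is a problem, and neither planned analysis changes it.

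**2. Reproduce the plan's power.** Inputs from Protocol 9.1: "The recommended sample size for the study is 150 evaluable patients per group", response rates of 60% (CC) and 73% (DS), a rule described as "analogous to 1-sided p-value < 0.05", and stated power of 0.77.

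- Pooled SE = √(2 × 0.665 × 0.335 / 150) = 0.0545
- Unpooled SE = √((0.60 × 0.40 + 0.73 × 0.27) / 150) = 0.0540
- z = (0.13 − 1.645 × 0.0545) / 0.0540 = 0.7475, so power = Φ(0.7475) = 0.773

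This agrees with 0.77. The simple two-proportion approximation, without center or baseline terms, is adequate for what follows.

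**3. Weight of one patient.** With 330 randomized 1:1 there are 165 per arm. One patient is 1/165 = 0.6 points (1/150 = 0.67 points on the evaluable number). Three patients are 3/165 = 1.8 points, against a planned effect of 13.

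**4. Error rate if there is no true effect.** Suppose both arms are at 60%, with 150 per arm, and k DS patients are scored as responders instead of failures. The formula of step 2 with DS rate 0.60 + k/150 gives:

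| k | Added to DS rate | One-sided false-positive rate |
|---|---|---|
| 0 | 0 | 0.050 |
| 1 | 0.67 points | 0.063 |
| 2 | 1.33 points | 0.080 |
| 3 | 2.00 points | 0.099 |
| 5 | 3.33 points | 0.147 |
| 8 | 5.33 points | 0.245 |

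The documents do not give k. The range is an assumption, set against about 15 planned early exits per arm (10% dropout, all causes), and it assumes that every such patient meets the responder definition.

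**5. Effect on the decision.** Use a normal approximation on the log-odds scale, with CC at 99/165 (60%).

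- Near the threshold: DS 113/165 gives (0.776 − 0.405) / 0.231 = 1.605, posterior probability 0.946. DS 114/165 gives 1.722, probability 0.958.
- At the planned effect: DS 120/165 (73%) gives z = 2.44, probability 0.993. With three fewer responders, 117/165 gives z = 2.08, probability 0.981, still above 0.95.

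So a few such exits matter only when the result is close to the threshold.

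**The case against.** Much of the case on the other side stands.

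- **The exception is limited.** It covers only events judged not severe enough to stop for. A reader might infer that any adverse-event exit involving another SABA escapes the failure rule. It does not: the default for multiple reasons is still the adverse event.
- **The trigger is limited.** Systemic corticosteroids, a LAMA or a biologic are recorded management actions, not prohibited drugs.
- **Disease worsening is a separate listed reason.** Protocol 4.3 moves the label away from the adverse event; it does not say that worsening stops being a reason. The SAP does not say whether the CRF reason or the narrative decides. The escape is therefore permitted by the text rather than required by it, and that ambiguity is what needs closing.
- **Withdrawal may not follow.** Protocol 4.3 makes it mandatory, while Appendix C lets the sponsor allow a patient with such a deviation to continue. The two passages need to be reconciled.
- **Safeguards exist.** A missing ET visit already means failure, and rescue use is one of the five ACT items, so extra SABA use should lower the score.
- **Some of it will be visible.** Withdrawal reasons are tabulated (SAP 5.2) and the ET visit is summarized separately (SAP 4.4). That would show how many such exits occurred, but would not test their effect.

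A reader might also conclude that the exit rules as a whole favor DS. The documents do not support that: technology failure and dislike of the platform can in practice occur only in DS, and both count against it. Nor do they support failing every DS exit for noncompliance with the eMDPI. Such an exit need not reflect a clinical event, the drug is taken as needed, and the penalty would fall on one arm only.

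**Conclusion.** The gap is real and narrow. Under the current text, a DS patient whose exit was triggered by an adverse event or asthma worsening can be scored as a responder on an early ACT because of how the reason is recorded. CC has no corresponding route, and the one planned sensitivity analysis does not examine it.

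This route, taken alone, can only raise the DS rate, by about 0.6 points per patient. The direction of bias over all exit rules is not determined. If three patients were affected and there were no true effect, the nominal 0.05 error rate would be about 0.10. At the planned effect, three patients would not change the conclusion. The 113-to-114 switch only locates the threshold and is not evidence that the result would turn on it.

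These figures rest on an assumed number of exits, on each patient meeting the responder definition at the ET visit, and on approximations without center or baseline ACT. The 1/165 figure also assumes that all randomized patients enter the mITT set. The point deserves a SAP clarification before database lock; it is not a reason to doubt the design.

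**What to change.** 1. In SAP 4.3 and 6.2.2, state that exits recorded as need for a prohibited medication are classed by the underlying event. Those triggered by an adverse event or asthma worsening count as treatment failures; any others keep the ET rule.
2. In SAP 6.2.3, treat the exits so classed like the other listed reasons, that is, as missing and imputed.
3. Add one sensitivity analysis that counts every early discontinuation, in either arm, as a failure. It does not depend on the recorded reason.

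The classification needs only the CRF reason and the withdrawal narrative that Protocol 4.3 already requires. It should be fixed before exit reasons are tabulated by arm. The cost is SAP wording, one extra run and possibly a slightly lower DS response rate. Data collection, patient management and sample size do not change.

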4.4. Replacement of Patients

A patient who is enrolled but does not complete the treatment period will not be replaced.

4.5. Rescreening

A patient who is screened but not enrolled within 7 days of screening, because he/she did not satisfy inclusion/exclusion criteria or enrollment did not occur within the specified time, may be considered for rescreening once if, for example, there is a change in the patient’s medical background or a modification of study inclusion and exclusion criteria.

Patients may have individual parameters retested at the discretion of both the investigator and the sponsor.

If the patient is rescreened, the informed consent form (ICF) will need to be re-signed.

4.6. Screening Failure

Screening failures are defined as participants who consent to participate in the clinical study but are not subsequently enrolled in the study. Minimal information includes, but is not limited to, demography, screening failure details, eligibility criteria, and any serious adverse events.

5. TREATMENTS

5.1. Investigational Medicinal Products Used in the Study

The Teva eMDPI Digital System consists of 4 devices. Device 1 is the Albuterol eMDPI, which is the test IMP. The 3 investigational medical devices are the following:

- Device 2: Patient-facing App
- Device 3: DHP (Cloud solution)
- Device 4: Provider-facing dashboard

At Visit 1, patients in the DS group will be trained on the use of the Albuterol eMDPI DS (including instructions on how to use both the eMDPI and the App) and, upon demonstrating competency, will receive 2 Albuterol eMDPI devices for use as rescue bronchodilators to replace their rescue treatment during the study. Additional Albuterol eMDPI devices may be supplied during the treatment period, based on patients' needs. Patients will be instructed to return all inhalers to the investigational center at the end of treatment visit or at early termination.

5.1.1. Test Investigational Medicinal Product

[figure not shown]
Albuterol eMDPI (marketed in the US as PROAIR DIGIHALER) is an inhalation-driven eMDPI containing a blend of albuterol sulfate and alpha-lactose monohydrate. The inhaler contains 200 actuations, each delivering 90 mcg of albuterol base ex-mouthpiece; the inhaler is equipped with a dose counter that shows only even numbers and counts down to “0.”

The plastic inhaler comprises a reservoir containing inhalation powder, a metering system, a mouthpiece with dust cover, and an eModule sitting on top of the drug-delivery compartment. Teva has developed the eModule as part of a system to assist a patient with asthma to appropriately use the eMDPI inhaler. The system is described in more practical terms as an inhaler with an integrated data logger capable of storing and transmitting timestamped data to support the data logging functionality.

The on-board electronics and power source are fully integrated into the eMDPI and are designed to operate for the life of the inhaler without intervention, ie, the battery does not require replacement or recharging.

The addition of the required electronics has no impact on the pharmaceutical performance of the inhaler or on the required user steps to take a dose. A schematic of the inhaler with the additional eModule is shown in [Figure 3](#).

Figure 3: Current Inhaler (Left) Versus Inhaler with Additional Electronics Module (Right)

Additional details may be found in [Table 4](#) and in the IB.

The information from the eModule may be transmitted wirelessly (Bluetooth Low Energy) to an App. From the App, data may be transmitted to the DHP, which consists of a Cloud solution, and then to a dashboard. This allows the patient and/or the caregiver to track when and how well the inhaler was used.

By consenting to enroll in the study, the patient must also download the smart device App (with the assistance of investigational center personnel), accept the smart device App's Privacy Notice and Terms of Use, and also agree to share his/her data to a provider-facing dashboard utilized by the iHCP and investigational center study team. An ICF will be provided to the patients which will elaborate, among other ways, Teva's ways of use and storing of patient data collected through the smart device App. The patient will be entering into a direct contractual relationship with Teva which will govern, among other things, Teva's rights to use and store patient data collected through the smart device App. If the patient does not accept the smart device App's Privacy Notice and Terms of Use and does not also agree to share their data to the provider-facing dashboard utilized by the iHCP and investigational center study team, then the patient cannot enroll in the study. At the end of treatment/ET visit (Visit 2), investigational center personnel will remove the App from the patient's smart device.

